## 8.2 Subject Disposition

The following subject disposition information will be summarized in the Safety population except otherwise noted.

- Number of treated subjects (Safety Population)
- Number of subjects who completed study treatment (did not permanently withdraw treatment as indicated on study drug administration eCRF)
- Number of subjects who discontinued study treatment
- Number of subjects who completed study
- Number of subject who discontinued from study
- Primary reason for study discontinuation (withdrawal of consent, discretion of the investigator, lost to follow-up, or other)

Other subject listings will include a listing of inclusion and exclusion criteria violations.

## 8.3 Demographic and Baseline Characteristics

### 8.3.1 Demographic and Baseline Characteristics

The demographic variables collected in this study include age, sex, race, and ethnicity. Subjects who record more than one race will be grouped into a single category denoted as multi-racial. Additionally, the number (%) of subjects who are on background pirfenidone, nintedanib, or either on pirfenidone or nintedanib and the number (%) of subjects whose baseline flow rate was  $\leq 4$  L/min O2 or  $> 4$  L/min O2, will be presented.

Age (years) will be summarized using continuous descriptive statistics. Age will be reported in years as per the eCRF.

Demographic variables will be summarized for the Safety population.

### ***8.3.2 Targeted and Other Medical History***

Targeted medical history events will be summarized (n, percent) by the event type for the Safety population. The targeted medical history events that will be summarized are as follows:

- Cancer history
- Inflammatory/autoimmune disease
- Primary hypertension (including grade of severity and medication taken)
- Pulmonary rehabilitation
- Gastroesophageal reflux (including medication taken)
- Sleep disordered breathing/sleep apnea (including CPAP, surgeries, medication taken)
- Pulmonary embolism (including medication taken)
- Lactose intolerance (including medication taken)

Disorders recorded on the other medical history eCRF will be mapped to a preferred term (PT) and a system organ class (SOC) using the Medical Dictionary for Regulatory Activities (MedDRA, Version 20.0). Other medical history events will be summarized by SOC and PT for the Safety population. If a subject has more than one event within a SOC, the subject will be counted only once in that SOC. If a subject has more than one event that codes to the same PT, the subject will be counted only once for that PT.

### ***8.3.3 Prior and Concomitant Medications***

All prior and concomitant medications will be coded using WHO Drug Dictionary Enhanced March 2017. Concomitant medications are defined as medications with start date or end date on or after the date of first dose and start date before the date of the last dose + 30 days or are ongoing at the time of first dose. Prior medications are defined as medications with a stop date before the date of first dose of study drug.

Prior and concomitant medications will be listed only.

## **8.4 Safety Analysis**

All safety analyses will be based on the Safety population.

### ***8.4.1 Study Drug Administration***

The following measures of overall extent of GBT 440 includes:

- Extent of exposure (days), defined as (date of last dose – date of first dose + 1)
- Number (%) of subjects with drug permanently discontinued
  - Reasons for discontinuation (Adverse event, Other)

- Number (%) of subjects with at least one dose missed
  - Number of subjects grouped by number of doses missed (0,1, etc.)
- Number (%) of subjects with at least one dose reduction
  - Number of subjects grouped by number of dose reductions (0,1, etc.)
  - Reasons for dose reduction (AE or Other)
- Number (%) of subjects with at least one dose interruption
  - Number of subjects grouped by number of dose interruptions (0,1, etc.)
  - Reasons for dose interruption (AE or Other)

#### **8.4.2 Study Drug Compliance**

Dosing compliance (% compliance) will be assessed by calculating the number of actual doses received and comparing that to the number of expected doses as follows.

$$\text{Compliance (\%)} = \frac{\text{Number of Actual Days Dosed}}{\text{Number of Expected Days Dosed (days)}} \times 100\%$$

The actual days dosed is defined as the sum of the days a subject was dosed. The number of expected days dosed (date of last dose – date of Day 1 +1) that will be used for calculating dosing compliance.

#### **8.4.3 Adverse Events**

Each reported AE term will be mapped to PT and SOC using the MedDRA Version 20.

Treatment-emergent adverse events (TEAEs) are defined as any event that occurs or worsens on or after the first dose of study drug and within 30 days after the last dose. Treatment-emergent adverse events (TEAEs) will be summarized based on the number (%) of subjects experiencing events by SOC and PT. The denominator for the percentage will be based on the number of subjects in the Safety population (i.e., those that received at least one dose of study drug).

A subject reporting the same AE more than once will be counted only once when calculating incidence 1) within a given system organ class, and 2) within a given system organ class and preferred term combination. For such cases, the maximum CTCAE toxicity grade and strongest causal relationship to study treatment for the event will be used in the incidence calculations.

An overall summary will be presented that includes the number of TEAEs and the number and percentage of subjects who experienced at least one TEAE. This summary will also include TEAEs  $\geq$  Grade 3, TEAEs possibly/probably related to study drug, serious adverse events (SAEs), TEAEs leading to discontinuation of study drug, and deaths.

Summaries of the following TEAEs will be provided by SOC and PT:

- All TEAEs
- Treatment-related AEs
- TEAEs by maximum severity, table includes a summary of AEs grade 3 or higher
- Serious TEAEs (AE listing)
- TEAEs that led to dose modification or permanent discontinuation of GBT 440 (listing only )

Summaries presented by SOC and PT will be ordered alphabetically for SOC and descending frequency within SOC of PT based on the total GBT 440 group.

All AE data will be summarized for each dose level (900 mg, 1500mg).

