6.3 Study Drug Discontinuation

Subjects should discontinue study drug for any of the following reasons:

- Malignancy: not including local and non-serious basal or squamous cell skin cancer
- Pregnancy
- Anaphylaxis, anaphylactoid or serious hypersensitivity reaction
- Grade 3 or higher rash
- Use of any medication to treat IPF, other than those documented at screening.
- AE, which in the opinion of the Investigator, precludes the subject from safely continuing in the study
- Pulmonary rehabilitation started at any time from screening until the end of the study
- Subject is noncompliant with study requirements

The date and reason for discontinuation should be documented in the eCRF.

Subjects who discontinue study drug *should continue in the study to complete all scheduled assessments.*

Those subjects who are unwilling or unable to complete all remaining scheduled assessments should return to the site to complete the Early Termination visit assessments within 2 weeks (± 7 days) from the date of discontinuation. In this way, all subjects will be assessed at least 5 half-lives after the last dose of study drug.

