10.1 Adverse Events (AE)

An AE is defined as any untoward medical occurrence in any subject enrolled in a clinical investigation administered a pharmaceutical product, -regardless of causal attribution.

An AE can be any unfavorable and/or unintended sign, symptom, or disease temporally associated with the use of an investigational product, whether or not it is thought to be related to the investigational product. In addition to new events, any increase in the severity or frequency of a pre-existing condition that occurs is considered an AE. This includes any side effect, injury, toxicity or sensitivity reaction.

Subjects will be monitored throughout the study for AEs, from the time informed consent is obtained until the last study visit (Day 120). Reporting of AEs prior to enrollment should only include SAEs or AEs resulting from any protocol-related interventions.

AEs that are identified at the last assessment visit as specified in the protocol must be recorded in the eCRF. All events that are ongoing at this time will be recorded as ongoing on the eCRF. All (both serious and non-serious) AEs must be followed until they are resolved or stabilized, or until reasonable attempts to determine resolution of the event are exhausted. The Investigator should use his/her discretion in ordering additional tests as necessary to monitor the resolution of such events.

All reported AEs will be coded using the current version of the Medical Dictionary for Regulatory Activities (MedDRA).

All procedures specified in [Section 10.3](#) are to be followed for reporting SAEs.

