11 DATA ANALYSIS AND STATISTICAL PLANS

This section describes the statistical methodology to be used in the analysis of the protocol endpoints. Details of all planned analyses will be specified in a separate Statistical Analysis Plan (SAP).

Data will be summarized using descriptive statistics. Continuous variables will be summarized using mean, standard deviation (SD), coefficient of variation (CV%, as appropriate), median, minimum, maximum, and, as appropriate, geometric mean. Categorical variables will be summarized by presenting the number (frequency) and percentage in each category.

Data will be summarized by dose level (900 mg, 1500 mg) and overall (total subjects). All collected data will be presented in data listings.

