11.3 Statistical Analyses

11.3.1 Efficacy Analyses

The analysis of the primary and secondary endpoints will be summarized descriptively. Each endpoint will be summarized by dose group and overall (total subjects).

Full details of the analysis methods, including how missing data will be handled, will be provided in the SAP.

11.3.2 *Safety Analyses*

Safety and tolerability will be assessed by incidence, severity and changes from baseline of all relevant parameters including AEs, laboratory evaluations, vital signs, and ECGs.

AEs will be coded using the Medical Dictionary for Regulatory Activities (MedDRA). The number and percentage of subjects experiencing 1 or more AEs will be summarized by dose group and overall, relationship to study drug and severity according to system organ class and preferred term. Additional summaries will be provided for SAEs and events resulting in permanent discontinuation of study drug.

Laboratory parameters will be summarized using descriptive statistics and by post-dose shifts relative to baseline. Laboratory values outside normal limits will be identified in the subject listings and will include flags for high and low values.

Vital sign results and ECGs will also be summarized descriptively for each scheduled protocol time point.

11.3.3 *PK and PK/PD Analyses*

A listing of PK sample collection times as well as derived sampling time deviations will be provided. A subject listing of all concentration-time data for each treatment, and study day will be presented. PK variables will be summarized using appropriate descriptive statistics (e.g., n, mean, SD, CV%, minimum, median, and maximum, and/or geometric mean) by part, dose, and study day.

Graphical presentations of key PK parameters and concentrations will be used as appropriate. Figures of individual concentrations versus time will be presented by subject.

PK/PD analyses will be performed.

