- a. All screening evaluations must be completed and reviewed prior to Day 1 (Visit 2) to confirm the subject meets all eligibility criteria prior to dosing.
- b. All subjects who discontinue study or study drug prior to study completion and who are unwilling or unable to complete the remaining scheduled visits should return to the study site to complete all ET assessments (see [Section 6](#))
- c. Written informed consent must be obtained and documented prior to performing any study-specific screening procedure
- d. Demographics, medical history and baseline conditions obtained at screening should be reviewed again and any changes since screening noted in the eCRF
- e. After informed consent but prior to randomization only SAEs resulting from a protocol-mandated intervention should be reported. After randomization, all adverse events will be reported until study completion (Day 120).

- f. Includes evaluation of the head, eyes, ears, nose and throat and cardiovascular, respiratory, musculoskeletal, gastrointestinal, neurological, dermatologic systems. No rectal or pelvic examination is required. Record any observed abnormalities in the eCRF. At subsequent visits record new or worsened clinically significant findings on the eCRF.
- g. Perform a limited, symptom-directed examination as clinically indicated. Record new or worsened clinically significant findings in the eCRF.
- h. Includes heart rate, respiratory rate, systolic and diastolic blood pressure and temperature measured in a semi-recumbent or supine position and resting for at least 5 minutes.
- i. Performed at the time of Vital Signs assessment, with the subject breathing their supplemental O2 delivered at the usual prescribed rate and after the subject has rested for at least 5 minutes.
- j. Perform 12-lead ECG after the subject has been resting in a semi-recumbent or supine position for at least 5 minutes.
- k. Perform for all female subjects who are not post-menopausal or surgically sterile. On Day 1, urine pregnancy must be performed before any other assessments. The Investigator is to ensure that the result is negative prior to completing any other study related assessments and prior to administering investigational product to the subject.
- l. If a urine pregnancy test on Day 1 is positive, confirm the result with a serum pregnancy test. The serum pregnancy test must be available (and negative) prior to Day 1 dosing.

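### SAP 8.4.3 ends its SOC/PT tables and its named serious-event listing 30 days after last dose, while the protocol collects AEs to Day 120, so a late SAE or death in a subject who stops drug early may go unlisted

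*SAP*

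**What the plan says.** **Protocol: collection.** Section 10.1 monitors adverse events "from the time informed consent is obtained until the last study visit (Day 120" and the schedule footnotes in Appendix A give the same end. That end is a study day and does not depend on the last dose. Under 6.3, subjects who stop study drug should "continue in the study to complete all scheduled assessments"; sections 8.3.2 and 8.5.3 repeat this.

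**Protocol: presentation.** Section 11.3.2 plans: "The number and percentage of subjects experiencing 1 or more AEs will be summarized by dose group and overall". It then adds: "Additional summaries will be provided for SAEs and events resulting in permanent discontinuation of study drug". Neither sentence carries a treatment-emergent limit, and neither gives an end date. Section 11 says: "All collected data will be presented in data listings". The safety endpoint in 3.2.4 is framed as TEAEs, but the protocol gives no TEAE window.

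**SAP.** Section 8.4.3 defines a TEAE as "any event that occurs or worsens on or after the first dose of study drug and within 30 days after the last dose". The outputs by system organ class and preferred term (SOC/PT) all sit under a TEAE heading, including the serious-event item, "Serious TEAEs (AE listing". The overall summary in the same section covers TEAEs of Grade 3 or higher, related TEAEs, SAEs, TEAEs leading to discontinuation, and deaths. Three of these five items carry the TEAE qualifier; SAEs and deaths do not. Section 8.1 commits to listing eCRF data that appear in a summary table, and 7.1 defines days since last dose for use in adverse event listings.

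**The concern.** The two documents run on different clocks. The protocol's clock ends at a fixed study day; the SAP's TEAE clock ends at a fixed interval after the last dose. They agree for a subject who takes the full course and diverge for one who stops early and remains on study.

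That subject matters for safety. The reasons for stopping drug in protocol 6.3 include an adverse event that rules out safe continuation and the use of IPF medication not documented at screening. Such subjects are plausibly sicker than average, though the documents give no data on this. The study has no control arm, protocol 1.5.4 acknowledges a theoretical risk of tissue hypoxia, and this SAP specifies only the safety analyses for an abbreviated report. Its safety outputs are therefore the main place where a late serious event would be seen.

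At stake is whether an SAE or death that the sites have collected is sure to appear in the report. As written, that depends on how a programmer reads one sentence.

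**Working it through.** **Inputs**
- End of adverse event collection: Day 120 (protocol 10.1 and Appendix A footnotes).
- TEAE window: last dose + 30 days (SAP 8.4.3).
- Treatment period: 90 days (protocol 8.1).
- Visit windows: ±5 days at both Day 90 and Day 120 (protocol Appendix A).
- Early Termination visit: within 2 weeks ± 7 days of discontinuation (protocol 6.2, 6.3).

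**Step 1: the plan's own figure.** For a full-course subject the window ends on Day 90 + 30 = Day 120, which matches the protocol's end of reporting. The nominal gap is 0 days.

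**Step 2: early stoppers who stay on study.** Uncovered days = 120 − (last-dose day + 30). Share of post-dose follow-up = uncovered days ÷ (120 − last-dose day).

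| Last dose | Window ends | Uncovered days | Share of post-dose follow-up |
|---|---|---|---|
| Day 15 | Day 45 | 75 | 75/105 = 71.4% |
| Day 30 | Day 60 | 60 | 60/90 = 66.7% |
| Day 45 | Day 75 | 45 | 45/75 = 60.0% |
| Day 60 | Day 90 | 30 | 30/60 = 50.0% |
| Day 75 | Day 105 | 15 | 15/45 = 33.3% |
| Day 90 | Day 120 | 0 | 0% |

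**Step 3: visit-window slack.** With the last dose at a Day 90 visit held on Day 85 and the final visit on Day 125, the gap is 125 − (85 + 30) = 10 days. This needs opposite extremes of two visit windows.

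**Step 4: subjects who leave early.** The Early Termination visit falls at most 14 + 7 = 21 days after discontinuation. That is inside 30 days if discontinuation is dated from the last dose, so these subjects normally have no gap. One who stops drug, stays for some time and then withdraws could still have one.

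**Step 5: follow one event through the outputs.** Take an SAE on Day 100 in a subject whose last dose was on Day 30. It is 100 − 30 = 70 days after last dose, and the TEAE window closed on Day 60.
- Protocol: collected (10.1), within the unqualified SAE summary (11.3.2), and to be listed (section 11).
- SAP SOC/PT tables: excluded.
- SAP serious-event listing: excluded, because it is limited to TEAEs.
- SAP overall summary, taken literally: counted in the SAE row. SAP 8.1 would then support listing it, but the named listing leaves it out, so the row and the listing disagree.
- SAP overall summary, with the TEAE window read in: not counted. The event is then in neither the summary nor the serious listing.

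**Step 6: illustration only.** The documents give no SAE rate. Assume a constant 30-day SAE risk r. The chance of at least one SAE in the 60 uncovered days of one subject who stops at Day 30 is 1 − (1 − r)². This gives 4.0% at r = 2%, 9.8% at r = 5% and 19.0% at r = 10%.

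**The case against.** The case on the other side is substantial, and several stronger readings fail because of it.

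- **A reader might infer that the SAP stops counting SAEs at 30 days.** The text does not say so. SAEs and deaths in the overall summary lack the TEAE qualifier that the neighbouring items carry, so the literal reading is that late ones are counted.
- **A reader might infer that the SAP lists nothing beyond serious TEAEs.** It also lists TEAEs leading to dose modification or discontinuation. Section 8.1 supports listing whatever a summary table shows, and 7.1 provides for adverse event listings with days since last dose and no 30-day cap. The protocol's promise to list all collected data also stands.
- **A reader might infer that the protocol summarises all AEs to Day 120.** Day 120 is its collection and reporting end. Section 11.3.2 states no end date, and the safety endpoint is TEAEs, so TEAE tables implement the protocol.
- **A reader might infer that each dose will look safer than it is, or express one missed SAE as a percentage of a 16-subject group.** The documents give no early-stopping rate and no late-event rate. The only SAE percentage the SAP plans is in the overall summary, which is unrestricted as written.

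The 30-day window also matches the planned 30-day safety follow-up, which both documents describe as at least 5 half-lives. Events beyond it are harder to attribute to the drug. That justifies the window for the TEAE tables. It does not justify leaving collected SAEs out of the serious-event listing, because a listing with days since last dose lets the reader judge attribution.

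Protocol 10.3.5 requires SAE reporting within 24 hours whatever the cause, so a late SAE would reach the safety department. That does not ensure that it appears in the study report.

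What remains is one stated exclusion, in the named serious listing, and one ambiguity, in the overall summary.

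**Conclusion.** The point holds as a mismatch between what the protocol collects and promises to list and what SAP 8.4.3 names as its serious-event output. For subjects who stop drug early and remain on study, 75, 60, 45 or 30 days of collected follow-up fall outside the SOC/PT tables and the serious listing for stops at Day 15, 30, 45 or 60. For a nominal completer the figure is zero.

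Loss of a late SAE or death from the whole report is possible but not stated: it requires the TEAE window to be read into the overall summary. Under the literal reading the defect is smaller, namely a count that the named listing cannot support.

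The size rests on two assumptions: that some subjects stop early, and that they stay to Day 120 as the protocol asks. The documents do not say how many will. The matter is worth settling before database lock because it concerns deaths and serious events and the correction is small.

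**What to change.** Keep the TEAE definition and the SOC/PT tables as they are. In SAP 8.4.3, replace the serious-event listing item with wording such as:

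> *All SAEs and deaths from first dose through the last study visit, listed with days since last dose and a treatment-emergent flag. The SAE and death rows of the overall summary cover the same period.*

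The events are already collected, and days since last dose is already defined in SAP 7.1. The flag follows from the existing TEAE rule. The cost is one SAP sentence and a slightly longer listing. With the change, uncovered days for SAEs and deaths fall to zero for every stopping day, and the summary rows and the listing can be reconciled with each other.

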#### ***8.4.4 Laboratory Data***

Actual values and change from baselines for all laboratory parameters will be summarized using descriptive statistics (serum chemistry, liver function tests, hematology, and serum erythropoietin) using SI units. Coagulation results will be listed only. Baseline is defined as the Screening measurement taken before the first dose of GBT440 for most labs. Baseline serum erythropoietin is Day 1.

A listing of all clinically significant laboratory values will be provided. Pregnancy results at each visit will be listed without summary. Listings will be presented with reported units and SI units.

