1.5.4 Potential Risk of GBT440 Treatment

Tissue Hypoxia

There is a theoretical risk of tissue hypoxia in subjects treated with GBT440 based on the mechanism of action and the potential for impairment in O₂ offloading at the tissues. However, in vitro data show that GBT440-modified Hb remains sensitive to the Bohr effect, and in vivo data from animal models of pulmonary hypoxemia are consistent with increased oxygen extraction and consumption by tissues. Furthermore, clinical data from subjects receiving study drug and those participating in maximal cardio-pulmonary exercise tests in the ongoing Phase I/II study, GBT440-001, have not identified a concern with tissue hypoxia. Please refer to the GBT440 IB for further details.

IPF subjects in this study will be closely monitored for subclinical evidence of worsening tissue hypoxia including using assessments for erythrocytosis, increased resting heart rate and erythropoietin and laboratory tests indicating organ injury (e.g., liver aminotransferases).

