5.4 Laboratory Examination

5.4.1 *Clinical Laboratory Studies*

It is the responsibility of the Investigator to assess the clinical significance of all abnormal clinical laboratory values as defined by the list of normal values on file for the local clinical laboratory. All clinically significant laboratory value abnormalities are to be recorded as AEs.

For the purpose of this study, a clinically significant laboratory value is any abnormal result that, in the judgment of the Investigator, is an unexpected or unexplained laboratory value and is accompanied by clinical symptoms and/or results in a medical intervention or corrective action (e.g., abnormalities that have clinical sequelae, require study drug dose modification, discontinuation of study drug, more frequent follow-up assessments or further diagnostic investigation). Any abnormal values that persist should be followed at the discretion of the Investigator.

Laboratory assessment time points are outlined in the Schedules of Assessments provided in Appendix A ([Table 15-1](#) for Part A; [Table 15-2](#) for Part B).

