## 8 STATISTICAL METHODS

### 8.1 General Considerations

Data will be summarized using descriptive statistics. Continuous variables will be summarized using mean, standard deviation (SD), median, minimum, and maximum. Categorical variables will be summarized by presenting the number (frequency) and percentage in each category. Minimum and maximum will be presented to the same decimal places as the collected data; means and medians will be presented to one additional decimal place than reported in the collected data. Standard deviations will be presented to two additional decimal places than reported in the collected data.

Change from baseline to post-baseline values will be calculated by subtracting the post-baseline value from the baseline value. The percentage change from baseline values to post-baseline values will be calculated using the following formula:

$$([post\text{-}baseline\ value - baseline\ value] / baseline\ value) \times 100\%$$

Data will be summarized by dose level (900 mg, 1500 mg) and all GBT440.

Individual subject data recorded on the electronic case report forms (eCRFs) presented in summary table will be presented in subject listings.

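### SAP 8.4.4 leaves out, without saying so, the laboratory shift summary and high/low flags that protocol 11.3.2 specifies

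*SAP*

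**What the plan says.** **Protocol.** Section 11.3.2 (Safety Analyses) states: "Laboratory parameters will be summarized using descriptive statistics and by post-dose shifts relative to baseline". It continues: "Laboratory values outside normal limits will be identified in the subject listings and will include flags for high and low values". The opening of section 11 adds a general rule: "All collected data will be presented in data listings".

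**SAP.** Section 8.4.4 states: "Actual values and change from baselines for all laboratory parameters will be summarized using descriptive statistics". It names serum chemistry, liver function tests, hematology and serum erythropoietin. Section 8.1 defines the statistics: "Continuous variables will be summarized using mean, standard deviation (SD), median, minimum, and maximum". Section 8.4.4 then adds: "A listing of all clinically significant laboratory values will be provided". Coagulation and pregnancy results are listed without summary. Section 8.1 also has a general rule that subject-level eCRF data behind a summary table will be listed.

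The SAP does not mention laboratory shifts, reference ranges or high/low flags in section 8.4.4 or anywhere else. Section 2 says that the SAP covers the safety analyses for an abbreviated report. It does not say that laboratory outputs were dropped for that reason.

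**The concern.** Protocol 1.5.4 names tissue hypoxia as the theoretical risk of the drug's mechanism and makes a specific commitment: "IPF subjects in this study will be closely monitored for subclinical evidence of worsening tissue hypoxia". The means it lists are erythrocytosis, resting heart rate, erythropoietin, and laboratory tests of organ injury such as liver aminotransferases. Most of these are laboratory markers, and the word subclinical means that the change may come without symptoms.

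The study is open label, has no control group, and enrolls up to about 16 subjects per dose. In that setting a safety reader looks for individual subjects whose markers leave the normal range. A shift summary and range flags are the outputs that show this directly, and they are the two that the SAP leaves out. A programmer who follows the SAP would produce a report without them, and nothing in that report would tell the reader that the protocol had specified them.

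**Working it through.** The point involves no sample size, power or error rate, so the check compares the two documents.

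**1. Specified against planned.**

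| Laboratory output | Protocol | SAP |
|---|---|---|
| Descriptive statistics | Yes (11.3.2) | Yes (8.4.4, 8.1) |
| Post-dose shifts relative to baseline | Yes (11.3.2) | Absent |
| High/low flags in listings | Yes (11.3.2) | Absent |
| Listing of individual values | Yes, all collected data (11) | Yes, for data behind summary tables (8.1) |
| Listing of clinically significant values | Not specified in 11.3.2 | Yes (8.4.4) |

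Two of the three items in protocol 11.3.2 are missing.

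**2. What the clinically significant listing covers.** Protocol 5.4.1 leaves the decision to the investigator. The value must be abnormal, must be unexpected or unexplained, and must be one that "is accompanied by clinical symptoms and/or results in a medical intervention or corrective action". The examples that follow include closer follow-up and additional diagnostic work. A symptom-free abnormality can therefore qualify if it prompts a repeat test. An abnormality with no symptoms and no resulting action does not have to be included.

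**3. Whether adverse event tables fill the gap.** Clinically significant laboratory abnormalities are recorded as adverse events (protocol 5.4.1 and 10.3.4). Those that are treatment-emergent are counted in SAP 8.4.3. This route passes through the same filter, so it adds nothing for abnormalities outside the definition.

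**4. What the remaining outputs show.** The minimum and maximum of the value and of the change will show an extreme result at full size. They do not show how many subjects shifted, or whether a value crossed its limit. Protocol 5.4.1 refers to normal values held for the local laboratory, and the synopsis allows up to 10 sites in two countries, so limits may differ between sites. A general listing without flags does not tell the reader which values are out of range. In addition, SAP 8.1 describes change as the post-baseline value subtracted from the baseline value. Taken literally, a rise appears as a negative change, while the percentage-change formula in the same section has the opposite sign. That makes the extremes of change easier to misread.

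**5. Whether the abbreviated report explains the omission.** SAP 8.4.6 keeps categorical counts for QTcF: above 450, 480 and 500 ms, and increases above 30 and 60 ms. Subject-level outlier counts therefore remain within the SAP's scope for ECG, but there are none for the laboratory markers of the named risk.

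**6. Whether the data exist.** Appendix A schedules hematology, chemistry and liver tests at screening and Days 30, 60, 90 and 120, and erythropoietin at Days 1, 30, 90 and 120. A baseline and several post-baseline values are planned for each.

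**The case against.** The strongest reply is that little is lost. The SAP reports five descriptive statistics, including minimum and maximum, for both value and change, and it lists the individual data behind them. Protocol 11 defers analysis details to the SAP. Protocol 1.5.4 concerns monitoring of subjects during the study and does not prescribe a table. Resting heart rate, named in the same sentence, is summarized at each scheduled visit under SAP 8.4.5. All of this stands, and it limits the size of the point. It does not account for two outputs named in the protocol disappearing without comment.

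Three stronger readings are tempting, and the documents do not support them:

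- **That the SAP lists only clinically significant values.** Section 8.4.4 does not call that listing the only one, and the rule in SAP 8.1 covers every summarized panel. Urinalysis is less clear: section 8.4.4 does not name it for summary, so SAP 8.1 does not plainly guarantee its listing, although protocol 11 does.
- **That the definition of clinical significance excludes subclinical change.** The protocol's own examples let in a symptom-free value that leads to follow-up or work-up. The accurate statement is that such changes need not be included.
- **That one subject's rise would vanish in a group mean.** The extremes are printed in the same table, so dilution of the mean does not measure what is lost.

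**Conclusion.** The point holds as an undeclared departure of the SAP from protocol 11.3.2. Two of three specified laboratory outputs are missing. As a result, no laboratory output counts subjects who move from normal to abnormal, and the only listing directed at abnormal values rests on investigator judgment. Abnormal values with no symptoms and no action would appear only unflagged in general listings and within group statistics.

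The size is modest. No data are lost, no efficacy conclusion is affected, and large individual changes would still show in the minimum or maximum. The change is worth making because the affected markers are those that the protocol ties to its named risk, and because it is cheap. The conclusion assumes that the general listing rule in SAP 8.1 is applied as written to all summarized laboratory panels, and that no separate table-shell document restores the two outputs.

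**What to change.** Add to SAP 8.4.4:

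- A shift summary relative to baseline, by dose level and for all GBT440, at least for hemoglobin/hematocrit, erythropoietin and liver tests. Classify values as low, normal or high against the reference range of the reporting laboratory, for example from baseline to worst post-baseline value. Keep the baselines already defined there (Screening for most tests, Day 1 for erythropoietin), and say whether Early Termination and unscheduled results count. Protocol 11.3.2 does not fix the categories, the analytes or the use of the worst value. These are suggestions, and the SAP should settle them before database lock.
- High and low flags on out-of-range values in the laboratory listings, as protocol 11.3.2 requires.

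If the sponsor intends to omit either output from the abbreviated report, the SAP should say so and give the reason.

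The cost is one standard table shell and a listing flag, using data already collected. This assumes that reference ranges are held with the laboratory results, which the flags promised in the protocol would need in any case.
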